## Study Protocol

**Subject Selection:** This project is designed as a prospective, single-center observational study. The cohort will consist of 250 consenting subjects  $\geq$  65 years of age who present to the BWH Weiner Center for Preoperative Evaluation (CPE) prior to elective lower extremity joint replacement surgery. These surgeries are selected because they are common in this age group, associated with significant morbidity, and along with dementia are considered a priority area (bone and joint conditions) by AHRQ. These ages are chosen as significant clinical data demonstrate increased cognitive impairment in community dwelling elders. Eligibility criteria include: patients  $\geq$  65 years of age with an ASA physical status of I-IV presenting for elective joint replacement or non-cancer spine surgery. Exclusion criteria will include planned ICU admission postoperatively, history of stroke or brain tumor, uncorrected vision or hearing impairment (unable to see pictures or read or hear instructions); limited use of the dominant hand (limited ability to draw); and or inability to speak, read, or understand English.

**Subject Enrollment:** The Brigham and Women's Hospital is the only study site. Study staff will use the CPE computerized scheduling system, which is updated continuously in real time and captures relevant information such as age and procedure, to identify potential subjects. When patients check in with the receptionist in the CPE for their appointment, they will be notified that they (and their surrogate) may be eligible to participate in a study in the CPE involving patients over the age of 65 or between the ages of 45-60. The receptionist will then provide them with a brochure about the study that includes information about the purpose of the study, the risks to the patient, and the potential benefits to society. The patient will then be asked if they are willing to speak with one of the study investigators and only those patients that agree to speak with a study investigator will be approached. Patients with known cognitive impairment will be included in the study to determine whether this information is included in the preoperative evaluation form. They will sign their own consent if they are capable and going to sign their surgical procedure consent. In the event that the patient is not capable of signing their own consent a surrogate will be asked to provide consent with assent from the patient. In our prior studies with similar patient populations less than 1% had documented cognitive impairment. The staff member will then describe the goals and risks of the study in a quiet room in the PATC and ask the patient (and their surrogate where appropriate) if they choose to participate. After all questions have been answered and the patient has the opportunity to read the consent form, written consent will be obtained by one of the study investigators.

**Study Procedures:** After obtaining consent, study staff will gain information about the patient's age and years of education. Study staff will administer standard instruments to assess mood (Geriatric Depression Scale-Short [GDS], a 15-item self-report questionnaire), social support (MOS Social Support Survey, a 12-item self-report questionnaire), alcohol consumption (Alcohol Use Disorders Identification Test—Consumption [AUDIT-C], a 3-item self-report questionnaire), and health and functional status (basic and instrumental activities of daily living [ADLs and IADLs, respectively, and the WHODAS]). The World Health Organization Disability Assessment Schedule 2.0 (WHODAS) is an alternative to the SF36 to measure physical health and disability. The Brief Pain Inventory (Short-Form) will be administered to assess pain before surgery. Grip strength will be measured with a JAMAR hand dynamometer as an index of frailty. In addition, patients will be asked if they've had a fall within the last 6 months, whether they've been evaluated for a change in memory or thinking, who accompanied them to their appointment, their employment status and their living situation (alone, institutionalized, living with family members) in a patient survey. The study staff will also administer the MiniCog, a simple cognitive screening tool that takes just 2-4 min to

complete and has little or no education, language, or race bias. In addition, the Animal Fluency test will be administered, which is a short cognitive screen that takes one minute to complete. Other measures of cognitive impairment will be obtained by study staff through: documentation on the patient's standard preoperative form, patient or informant report of diagnosis or evaluation for cognitive impairment or memory concerns, and systematic medical record review. During their routine preoperative blood draw the phlebotomist will be provided with one 10mL heparinized blood tube, one 5mL heparinized blood tube and one 5mL non heparinized blood tube labeled with only the patient's study ID number that will be returned to the investigative team and processed within 30 minutes of the blood draw. If the phlebotomist is not able to obtain a sample during the patient's preoperative appointment, a sample will be drawn by a study staff member trained by one of the anesthesiologists, or a nursing or physician member of the anesthesiology team prior to incision instead. 20mL of blood will also be obtained after surgery in the PACU and also on postoperative day 1 by a study staff member trained by one of the anesthesiologists, or a nursing or physician member of the anesthesiology team. Total, the proposed collection is 60mL. However, the additional 20mL blood sample on post-op day 1 will only be collected if the Hematocrit level is 0.30 or higher. Briefly, half of the sample would be spun down and plasma harvested and stored at -80 degrees C and when an adequate sample size obtained used to measure inflammatory cytokines by ELISA. The remainder of the sample will be divided into 1-ml aliquots and incubated at 37°C for 15 min with phosphatebuffered saline (PBS) (control), 100 ng/ml interleukin (IL)-6, 100 ng/ml IL10, or a combination of 100 ng/mlIL-2 and 2 ng/ml granulocyte macrophage colony-stimulating factor, or 1g/ml lipopolysaccharide. Blood samples will be resuspended in 1.4 ml stabilizing buffer and incubated for 10 min at room temperature for fixation in PFA, cooled to 4C, and stored at 80C until further processing for flow cytometry to determine the immune response of the white blood cells to a ex-vivo immune challenge and whether these correlate with Mini-Cog score or the development of delirium. Each enrolled patient will receive a business card listing the investigators' contact information and be advised to expect a follow up telephone call prior to surgery to assess cognitive function and at 6 months and 1 year after surgery to verify data elements and reassess functional outcome. Delirium will be assessed prospectively twice per day (early afternoon, early evening) on postoperative days 1, 2, and 3 by a trained study team member using the Confusion Assessment Method [CAM]. Delirium is most common on postoperative days 1-3. For functional status, the WHODAS will be administered 6-12 months postoperatively, along with the Geriatric Depression Scale to assess mood, either by personnel in the surgeon's office as part of routine follow up or by study staff or by telephone. We will also collect information on secondary outcomes including duration of PATC visit, presence of an advanced directive, whether they had surgical procedure, time to PACU discharge, discharge to place other than home (rehabilitation, skilled nursing facility), hospital length of stay (LOS), in hospital complications, perioperative variables including drugs administered, BIS, estimated blood loss, blood transfusions, fluid administered, blood pressure, oxygen saturation, 30-day reoperation or readmission rate, and 30-day and 1-year mortality. These outcomes are recorded in the medical record, the BWH Balanced Scorecard, an electronic database of all hospitalized patients that tabulates 31 elements of the hospital event, or the BWH Research Patient Database Enhanced Query. Data will also be confirmed by a follow up telephone interview. Thirty day and 1 year mortality will be recorded.

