
## Statistical Analysis Plan

As in our pilot study, we will define “likely cognitive impairment” as a score  $\leq 2$  on the MiniCog; while we are aware it is by no means a gold standard, it is based on a well validated cutoff that serves our purpose of identifying patients who may need special approaches during the perioperative period. All analyses will be repeated in the subset of individuals with the greatest degree of cognitive impairment based upon a MiniCog score of (0-1) in order to understand why these individuals were not identified as cognitively impaired. We will first test the sensitivity of standard procedures compared to systematic procedures with MiniCog defined impairment or severe impairment. We will also compare sensitivity and specificity of the standard vs. systematic approach, and vs. the published sensitivity of 75% in comparable populations. As a secondary outcome, we will try to understand the full relationship among our four assessments, for instance whether systematic chart review and patient/informant reports detect individuals not detected by standard MiniCog cutoffs, as such individuals would be important to include as part of a broad “impairment” outcome for Aim 2 and consider in subsequent work for special care in the perioperative period. Similarly, if we see patients who have received a formal evaluation of cognitive status in a memory clinic, by a primary care physician, or neuropsychological testing, we will try to understand qualitatively how MiniCog scores compare to such evaluations. Another secondary outcome will be how well patient/informant report can augment chart review when the patient does not have a primary care physician within our network. Differences between sensitivities and specificities will be compared using standard methods using confidence intervals. We will use logistic regression with any delirium as the outcome and cognitive impairment as defined by the MiniCog cutoff (or level of cognitive function as defined by the ordinal MiniCog score, modeled as best fits the data) in univariate analyses and in multivariate models adjusting for demographics (age, gender, education), baseline functional and medical covariates (ASA functional status, Charlson Comorbidity Index, METs, frailty). Analogous analyses for our secondary outcomes will use logistic, linear, or Cox proportional hazards models to assess the relationship of MiniCog scores to these outcomes. In univariate analyses, we will compare change in WHODAS in MiniCog-impaired vs. unimpaired patients using Wilcoxon U test and with ordinal MiniCog score using Spearman rank order correlation. Multivariate analyses will model change in WHODAS (ranked or transformed for best model fit) as a function of MiniCog impairment status (or ordinal value as above), controlling for age, gender, education, comorbidity index, and frailty. In exploratory analyses, patients with and without postoperative delirium will be analyzed separately and compared. Assays performed using blood collected from the current study will be analyzed in the grant “Circulating Extracellular Vesicles as Biomarkers of Postoperative Delirium” (grant submission number 1R21 AG061696-01). The grant has now received funding. [name], is the PI of the above grant; no changes to the current protocol will be made for this analysis. As a secondary analysis using variables collected during the course of the open enrollment phase of the study, a machine learning algorithm will be designed, to attempt to create a meaningful predictive model of postoperative delirium detection. This secondary use of data will explore the value of machine learning in anesthesiology, and its potential in predicting postoperative delirium.

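### The surgical cohort is defined in two conflicting ways, and if spine surgery is included the delirium and WHODAS models have no term for type of operation

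*Combined protocol and SAP*

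**What the plan says.** **Cohort.** Under Subject Selection, the opening description is of 250 consenting patients aged 65 or over attending the preoperative clinic "prior to elective lower extremity joint replacement surgery". The choice of these operations is justified partly because they "along with dementia are considered a priority area (bone and joint conditions) by AHRQ"; spine surgery is not mentioned. The eligibility sentence in the same paragraph then admits patients "presenting for elective joint replacement or non-cancer spine surgery".

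**Models.** In the Statistical Analysis Plan, the multivariable logistic model for any delirium adjusts for age, gender, education and "baseline functional and medical covariates (ASA functional status, Charlson Comorbidity Index, METs, frailty". The model for change in WHODAS is specified as "controlling for age, gender, education, comorbidity index, and frailty". The univariate WHODAS comparisons (Wilcoxon and Spearman) are not stratified. Models for the secondary outcomes are described only as analogous and have no covariate list of their own. No stratification, interaction or subgroup by operation appears anywhere.

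**Availability.** Subject Enrollment says that the scheduling system "captures relevant information such as age and procedure, to identify potential subjects".

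**A separate wording point.** The check-in notice in Subject Enrollment describes a study "involving patients over the age of 65 or between the ages of 45-60", while both sentences on the cohort require age 65 or over.

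**The concern.** The two definitions produce different screening lists, because staff find candidates by scheduled procedure. A spine patient is eligible under one sentence and outside the cohort under the other. That needs correcting whatever the analysis.

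The statistical consequence is conditional. Suppose spine patients are enrolled, and operation is related both to MiniCog status and to the outcome after the planned adjustment. The MiniCog coefficients would then absorb part of the difference between operations. The listed covariates describe the patient, not the operation, and the written models have no term with which to remove this effect or to show that it is absent. The claims at stake are that MiniCog status is associated with delirium and with functional change.

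**Working it through.** **1. Text.** The narrow definition is lower-limb joint replacement. The broad one is any joint replacement or spine surgery not for cancer. The second is not a subset of the first, so they cannot both define the cohort. The delirium model has MiniCog plus seven covariates (age, gender, education, ASA, Charlson, METs, frailty). The WHODAS model has MiniCog plus five (age, gender, education, comorbidity, frailty). Operation is in neither.

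**2. No figure to reproduce.** The plan gives N = 250 without an event rate, effect size, power or surgery mix. Every input below except N is therefore an assumption.

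**3. Crude odds ratio when MiniCog has no effect.** Assumed delirium risk is 5–10% after joint surgery and 15–20% after spine surgery. Assumed spine share is 40–60% among MiniCog-impaired patients and 30–35% among unimpaired patients. In each MiniCog group:

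risk = joint risk × (1 − spine share) + spine risk × spine share

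| Case | Joint / spine risk | Spine share, impaired vs unimpaired | Risk, impaired vs unimpaired | Crude OR |
|---|---|---|---|---|
| Mildest | 10% / 15% | 40% vs 35% | 12.0% vs 11.75% | 1.02 |
| Midpoint | 7.5% / 17.5% | 50% vs 32.5% | 12.5% vs 10.75% | 1.19 |
| Extreme | 5% / 20% | 60% vs 30% | 14.0% vs 9.5% | 1.55 |
| Reversed, furthest from 1 | 5% / 20% | 30% vs 50% | 9.5% vs 12.5% | 0.73 |
| Reversed, nearest to 1 | 10% / 15% | 30% vs 50% | 11.5% vs 12.5% | 0.91 |
| Equal mix | any | equal | equal | 1.00 |

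For the extreme case, (0.14/0.86) / (0.095/0.905) = 0.1628 / 0.1050 = 1.55. Of the 16 combinations of end-points, 11 give an odds ratio below 1.25.

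The extreme case is demanding. With 25% impaired, the overall spine share is 0.25 × 0.60 + 0.75 × 0.30 = 0.375. Impairment is then 0.15/0.375 = 40% in spine patients and 0.10/0.625 = 16% in joint patients.

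**4. False-positive rate.** Simulation under the null used 3000 datasets of 250 per case, 25% impaired and a nominal 5% Wald test. It compared a logistic model with MiniCog alone against MiniCog plus operation.

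| Case | Rejection without operation | Rejection with operation |
|---|---|---|
| Mildest | 4.2% | 3.8% |
| Midpoint | 6.5% | 3.7% |
| Extreme | 16.7% | 4.4% |

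In the extreme case the median odds ratio is 1.54 without operation and 0.99 with it.

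**5. WHODAS change.** For a linear model, bias = difference in spine share × operation effect. With an assumed operation effect of 0.2–0.5 SD and a share difference of 0.1–0.3, the bias runs from 0.1 × 0.2 = 0.02 SD to 0.3 × 0.5 = 0.15 SD.

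**6. Cost of the extra term.** The standard error of the MiniCog coefficient is inflated by 1/√(1 − φ²) − 1, where φ is the correlation between MiniCog status and operation. At 15–30% impairment φ is 0.04–0.28, giving 0.1% to 4.2% (in simulation, about 2% at the midpoint and 5% in the extreme case). Expected events are 250 × marginal risk: 250 × 0.0815 = 20.4 to 250 × 0.1425 = 35.6. Counting each covariate as one parameter, events per parameter fall from 2.5–4.5 (8 parameters) to 2.3–4.0 (9 parameters).

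**The case against.** The strongest reply is that the calculations do not test the criticised model. They compare MiniCog alone with MiniCog plus operation, whereas the plan adjusts for seven other variables that may account for much of any link between operation and MiniCog status. Residual bias after that adjustment has not been shown. This stands: the odds ratios are illustrations, not estimates of bias in the adjusted model.

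The assumed effect is also modest. At the midpoint the bias is log(1.19) ≈ 0.17 against a simulated standard error of about 0.47, roughly a third of one standard error. The 16.7% rejection rate needs every input at its extreme, and nothing in the documents supports so large a gap in impairment between operations. This stands too.

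If the MiniCog is meant mainly to flag patients at risk, the unadjusted association is of interest in itself. That is fair for the univariate analyses. It does not explain an adjusted model that controls for patient characteristics but not for the operation.

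Finally, the remedy adds a parameter to a sparse model, ASA may use more than one parameter, and a joint-versus-spine indicator leaves differences within each group untouched. These are real limits. They bear on how the term is used and do not support leaving it out of the two main models. Without the term the analysis cannot show whether operation matters, and adding it after results are seen is less credible than prespecifying it.

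**Conclusion.** The concern holds. The conflict between the two cohort definitions is plain in the text and rests on no assumption. So is the absence of an operation term from both covariate lists.

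The confounding is a possibility and has not been demonstrated. It requires that the broad definition applies and that operation is related to both MiniCog status and outcome after adjustment. Under the assumptions shown, the crude delirium odds ratio with no true effect lies between 1.02 and 1.55, or between 0.73 and 0.91 with the imbalance reversed. The WHODAS bias is 0.02 to 0.15 SD. With an equal mix there is no bias. The omission matters only if the imbalance is large, and its direction cannot be known from the documents.

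If the narrow definition applies, the joint-versus-spine issue does not arise. The analysis announced with "We will first test the sensitivity of standard procedures compared to systematic procedures" is unaffected either way. The 45–60 age wording is a separate inconsistency and adds no weight here.

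**What to change.** 1. State one surgical cohort definition, and make the opening description, the rationale and the eligibility sentence agree with it, including whether joint replacement is limited to the lower limb.
2. If spine surgery stays, prespecify type of operation (joint versus spine) as a covariate in the delirium and WHODAS-change models, and in secondary-outcome models where the event count allows. For rare outcomes such as mortality the term may not be estimable and need not be required; a penalised fit is an option where outcomes are sparse.
3. Separately, reconcile the 45–60 age wording in the check-in notice with the criterion of 65 or over.

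The cost is wording in the protocol and analysis plan, with no new data collection. The statistical price is one more parameter in a delirium model that may already have few events, with the small loss of precision worked out above.

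### The result of a past cognitive evaluation is not collected, so a patient evaluated and found normal can count as detected by the systematic approach

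*Combined protocol and SAP*

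**What the plan says.** Study Procedures introduces the non-MiniCog sources this way: "Other measures of cognitive impairment will be obtained by study staff through: documentation on the patient's standard preoperative form". The list continues with "patient or informant report of diagnosis or evaluation for cognitive impairment or memory concerns" and ends with a systematic review of the medical record. Among the patient survey items, the same section includes "whether they've been evaluated for a change in memory or thinking". It describes no question about the outcome of that evaluation.

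The SAP defines likely impairment as a MiniCog score of 2 or less, conceding that "it is by no means a gold standard, it is based on a well validated cutoff". Its first-listed comparison is: "We will first test the sensitivity of standard procedures compared to systematic procedures with MiniCog defined impairment or severe impairment". It then adds: "We will also compare sensitivity and specificity of the standard vs. systematic approach, and vs. the published sensitivity of 75% in comparable populations".

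The SAP does not say which sources make up the systematic approach, or what makes any source positive. It does refer to four assessments, and it speaks of chart review and patient or informant report as detecting people whom the MiniCog cutoff misses. Such people are to be considered for a broad impairment outcome in Aim 2. Where a formal evaluation is found, the SAP plans only a qualitative comparison with the MiniCog score.

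**The concern.** Having been evaluated is not the same as having been found impaired. A measure that accepts either, fed by a question that asks only about the first, cannot separate a diagnosed patient from one who was tested and cleared.

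The study wants to know whether systematic ascertainment finds impairment that the routine form misses. If the systematic approach accepts weaker evidence than the form, the comparison mixes two effects: looking in more places, and asking for less proof. In the first-listed comparison, which concerns sensitivity alone, a looser rule can only help.

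The consequence could also reach Aim 2. Cleared patients with a normal MiniCog would be false positives in the accuracy analysis, yet the SAP could treat the same patients as newly found cases and add them to the broad outcome.

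This is partly a data-capture problem. A missing coding rule can be written later, but a result that was never asked for may not be recoverable at analysis.

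**Working it through.** The plan states no figure on this point that could be reproduced, so the check is first one of text and then an illustration.

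**Text, side by side**

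1. *What is measured.* The Study Procedures list joins diagnosis and evaluation with an or, under the label of measures of cognitive impairment.
2. *What is asked.* The survey item covers having "been evaluated for a change in memory or thinking". No result is requested.
3. *What belongs to which approach.* The SAP's four assessments match the four sources in Study Procedures: MiniCog, preoperative form, patient or informant report, and record review. The MiniCog is the reference and the form is the standard procedure. That leaves report and record review as the systematic approach. This is an inference; the documents do not state it.
4. *What the form is tested for.* Subject Enrollment says that patients with known impairment are included to see whether that fact appears on the form. This suggests a test of recorded impairment, but no threshold for the form is written.
5. *What happens to a normal evaluation.* No section says it is scored as impaired, and none says it is not.

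**Illustration (all rates assumed)**

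Let *c* be the share of patients flagged only because of an evaluation with a normal result, or a concern, independently of MiniCog status. Then:

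- sensitivity after = sens + (1 − sens) × c
- specificity after = spec × (1 − c)
- Youden index after = (sens + spec − 1) × (1 − c)
- extra false positives = number unimpaired × spec × c

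The only input from the documents is N = 250. The assumptions are starting sensitivity 20%, starting specificity 98%, and a MiniCog-impaired share of 15%, 25% or 35%, which leaves 212, 188 or 162 unimpaired.

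For c = 5%: 0.20 + 0.80 × 0.05 = 0.240; 0.98 × 0.95 = 0.931; 0.180 × 0.95 = 0.171; with 188 unimpaired, 188 × 0.98 × 0.05 = 9.2.

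| c | Sensitivity | Specificity | Youden index | Extra false positives (212 / 188 / 162 unimpaired) |
|---|---|---|---|---|
| 0 | 20.0% | 98.0% | 0.180 | none |
| 2% | 21.6% | 96.0% | 0.176 | 4.2 / 3.7 / 3.2 |
| 5% | 24.0% | 93.1% | 0.171 | 10.4 / 9.2 / 7.9 |
| 10% | 28.0% | 88.2% | 0.162 | 20.8 / 18.4 / 15.9 |

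Sensitivity rises while discrimination falls. Under independence neither shift can exceed *c*, whatever the starting values, because the gain is (1 − sens) × c and the loss is spec × c.

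**The case against.** Four stronger readings are tempting, and the documents do not support them.

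- *A reader might infer that the plan scores a cleared patient as impaired.* It does not say so. Study Procedures lists sources and gives no scoring rule, so the plan permits this outcome without prescribing it.
- *A reader might infer that worry about memory alone counts.* That depends on how the phrase is parsed. It can equally mean a diagnosis or evaluation prompted by impairment or by concerns. No described survey item asks about concern alone.
- *A reader might infer that the form is held to a stricter threshold.* The form's threshold is undefined too. A note on the form of an evaluation or complaint might also count.
- *A reader might infer that the two approaches cannot be compared.* They can. Both are judged in the same patients against the same MiniCog cutoff, and specificity is compared as well: "We will also compare sensitivity and specificity of the standard vs. systematic approach". A looser rule would show up there.

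Two further objections carry weight. The documents attach the word systematic only to record or chart review; if that is the whole of the systematic approach, patient report is outside the lead comparison. And a patient who reports an evaluation and scores 2 or less is a correct flag against the study's own reference. A broader trigger may even be intended, since the stated purpose is to find patients who may need special handling around surgery.

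These objections limit the point without removing it. The specificity comparison would reveal a looser rule but could not say how much of the loss comes from cleared patients, because the result was not asked for. The chart may not supply it either: the SAP looks to patient or informant report when the primary care physician is outside the network, and there the chart is least likely to hold the result.

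**Conclusion.** The concern holds as a gap in data capture and definition. The plan does not collect the result of a past evaluation or define what counts as positive, so a patient found normal can be counted as detected. This can shift the systematic approach's sensitivity up and its specificity down relative to the form, and can place cleared patients in the broad Aim 2 outcome.

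The conclusion about the lead comparison assumes that patient or informant report is part of the systematic approach, which is likely but not stated. The route into Aim 2 does not need that assumption, because the SAP names such reports there directly.

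The size is unknown. In the illustration, with 2% to 10% flagged only this way, sensitivity moves by 1.6 to 8 points and specificity by 2.0 to 9.8 points, with about 3 to 21 extra false positives. If past evaluation is related to MiniCog status, the split between gain and loss will differ. The change is worth making because it is cheap and because the missing answer is hard to obtain afterwards.

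**What to change.** 1. Add one follow-up to the survey item: whether the evaluation found a problem or led to a diagnosis, with a do-not-know option. The telephone call already planned before surgery is another chance to ask.
2. Code the form, the patient or informant report and the chart on the same levels: (1) diagnosis, or evaluation that found impairment; (2) evaluation with unknown result; (3) concern only; (4) none, or evaluated and normal. An evaluation known to be normal is negative in every analysis, and unknown is kept apart from normal.
3. Name in the SAP the components of the standard and systematic approaches.
4. Report standard versus systematic sensitivity and specificity twice, with the same threshold applied to both approaches each time: level 1 only, then levels 1 to 3. Show the number at level 2, since patients who cannot recall a result are negative in the first row and positive in the second.
5. State which levels qualify a patient for the broad Aim 2 outcome.

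The cost is one question, some abstraction coding and one extra table row. The downside is that the systematic approach's sensitivity may look lower in the stricter row.

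### As worded, the non-home discharge outcome would count a facility resident's return to a facility as an event, and living situation is not among the listed covariates

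*Combined protocol and SAP*

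**What the plan says.** The outcome appears in the Study Procedures paragraph of the Study Protocol, in a list that opens "We will also collect information on secondary outcomes including duration of PATC visit, presence of an advanced directive". The item itself is "discharge to place other than home (rehabilitation, skilled nursing facility", so a skilled nursing facility is named, without qualification, as a destination that is not home. The source is routine data: "These outcomes are recorded in the medical record, the BWH Balanced Scorecard, an electronic database of all hospitalized patients", among others, with a follow-up telephone interview to confirm. No comparison with the patient's residence before surgery is described.

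That residence is collected. The same paragraph has staff record "their living situation (alone, institutionalized, living with family members) in a patient survey". Facility residents are not screened out. The Subject Selection paragraph begins its exclusions "Exclusion criteria will include planned ICU admission postoperatively, history of stroke or brain tumor, uncorrected vision or hearing impairment" and adds only limits on use of the dominant hand and on English. Under Subject Enrollment, "Patients with known cognitive impairment will be included in the study".

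For analysis, the Statistical Analysis Plan says: "Analogous analyses for our secondary outcomes will use logistic, linear, or Cox proportional hazards models to assess the relationship of MiniCog scores to these outcomes". The model this follows is the delirium model, run univariately and then adjusted for age, gender, education, ASA status, Charlson index, METs and frailty. Living situation is not on that list.

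**The concern.** The analysis asks whether a low MiniCog score goes with a worse course after surgery. A patient admitted from a nursing facility who returns there has had no change in residence, yet meets the outcome as worded. If residents are more common among MiniCog-impaired patients, which is plausible but not stated, the impaired group collects extra events that reflect where its members already lived. The univariate model has no protection against this, and the listed covariates are at best partial proxies for residence.

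The plan handles the same issue differently for function: it analyses change in WHODAS, which takes the starting state into account. Discharge destination has no such step, although its baseline counterpart is on file.

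A second, separate issue concerns patients from the community. Whether someone lives alone plausibly affects discharge to rehabilitation. If living alone also differs by MiniCog group, leaving it out of the adjusted model confounds the association, in a direction that cannot be known in advance.

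**Working it through.** The documents give no discharge rate, no share institutionalized or living alone, and no link between residence and MiniCog. There is no planned figure to reproduce. Every input below except N = 250 is an assumption, and all results are unadjusted.

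**Residents counted as events, no true MiniCog effect.** Let f1 and f0 be the shares of residents among impaired and unimpaired patients, and p the non-home discharge risk of everyone else, equal in both groups. All residents return to a facility.

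- Risk in each group = f + (1 − f) × p.
- Spurious OR = [R1/(1 − R1)] / [R0/(1 − R0)].
- Example, f1 = 5%, f0 = 1%, p = 0.2: R1 = 0.05 + 0.95 × 0.2 = 0.240; R0 = 0.01 + 0.99 × 0.2 = 0.208; OR = (0.240/0.760)/(0.208/0.792) = 1.20.

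The number of residents assumes 20% impaired, so 50 × f1 + 200 × f0. The odds ratios do not depend on that split.

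| f1 vs f0 | Residents of 250 | OR, p = 0.2 | OR, p = 0.4 | OR, p = 0.6 |
|---|---|---|---|---|
| 1% vs 0% | 0.5 | 1.05 | 1.03 | 1.02 |
| 2% vs 0.5% | 2.0 | 1.08 | 1.04 | 1.03 |
| 5% vs 1% | 4.5 | 1.20 | 1.10 | 1.07 |
| 10% vs 1% | 7.0 | 1.48 | 1.25 | 1.17 |

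With 50 against 200 patients, the chance of a falsely significant result in the harmful direction (nominal 2.5% in that tail) is 3–4% in the first two rows, 4–8% in the third and 7–21% in the fourth.

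**Restriction.** With residents left out, both groups have risk p, so the OR is 1.00 in this null scenario.

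**Recoding.** If returning residents stay in the denominator as non-events, risk = (1 − f) × p. For 10% vs 1%:

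- p = 0.35: 0.90 × 0.35 = 0.315 vs 0.99 × 0.35 = 0.3465; OR = (0.315/0.685)/(0.3465/0.6535) = 0.87. Counting them as events gives 0.415 vs 0.3565, OR 1.28.
- p = 0.50: 0.450 vs 0.495, OR 0.83. Counting them as events gives 0.550 vs 0.505, OR 1.20. Since 1/1.20 = 0.83, recoding only reverses the bias.

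**Living alone.** Assume 30% non-home discharge if not alone, an odds ratio of 2 to 4 for living alone, and 40% of impaired against 25% of unimpaired patients living alone.

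- Odds ratio 3: risk if alone = 3 × (0.3/0.7) / [1 + 3 × (0.3/0.7)] = 0.5625.
- Impaired: 0.40 × 0.5625 + 0.60 × 0.30 = 0.405. Unimpaired: 0.25 × 0.5625 + 0.75 × 0.30 = 0.366. OR = 1.18.
- Over odds ratios 2 to 4: 1.11 to 1.23. With the shares swapped (25% vs 40%): 0.81 to 0.90.

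**The case against.** The strongest reply is that the plan contains no rule scoring a returning resident as an event. Home is undefined and could be read as usual residence. That stands: a reader might infer a written coding rule, and there is none. But a skilled nursing facility is named as non-home without qualification, so an event is the likely coding. If abstractors read the term differently, coding will be inconsistent, which also calls for a definition.

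Second, residents may be very few. The surgery is elective, and Subject Enrollment reports under 1% documented cognitive impairment in the group's earlier studies. An answer option on a survey does not show that anyone will choose it. This also stands, and it is why the size is left open. The under-1% figure concerns documented impairment, however, so it bounds neither MiniCog-defined impairment nor the number of residents.

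Third, precision is low in any case. With 50 vs 200 patients and 35% risk, the standard error of the log OR is √(1/17.5 + 1/32.5 + 1/70 + 1/130) = 0.33, so the 95% interval spans a factor of exp(1.96 × 0.33) ≈ 1.9 either way. Every bias shown is smaller than that. Adjustment for age, frailty and comorbidity could also remove part of it. Both points limit the practical importance but do not justify an avoidable bias.

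Fourth, for pure prediction, omitting living situation is not an error, and the covariates for each secondary model are not spelled out. This is fair, so the univariate result should stay, and the covariate belongs only in the adjusted model.

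**Conclusion.** The concern holds in a limited form. On the plain wording, a return to a pre-surgery facility is an event. Such patients are eligible, their residence is recorded, and no listed step in the analysis accounts for it. The MiniCog association with this one secondary outcome could be biased upward. The spurious OR is nil without residents and about 1.02 to 1.2 if 1% to 5% of impaired patients (0% to 1% of unimpaired) are residents, with other patients' non-home discharge at 20% to 60%. The 1.48 in the table needs both the widest split in residence and the lowest base rate, and nothing in the documents makes that likely.

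Some stronger readings are not supported. A reader might infer that the association mainly measures prior residence; with no data on residence, that cannot be said. A reader might extend the argument to length of stay, through waiting for placement; no text or calculation supports it. The delirium and WHODAS analyses do not use this outcome and are unaffected.

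**What to change.** 1. Define home for this outcome, and analyse it only in patients not institutionalized before surgery, using the survey item already collected.
2. Report the number institutionalized at baseline by MiniCog group, so readers can see how much the restriction matters.
3. Do not recode returns as non-events. Defining the event as a move to a higher level of care looks equivalent to restriction but is not: it keeps returning residents in the denominator and biases the OR below 1. The survey item also does not separate types of facility, so levels of care cannot be ranked from it.
4. Add living alone versus with others to the adjusted discharge-destination model, and keep the univariate result for prediction.

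The cost is a few patients dropped from one secondary outcome (0.5 to 7 expected across the assumed scenarios), one degree of freedom, and a conclusion that applies to patients who lived in the community before surgery. No new data are needed.
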